2.10.2. Secondary outcomes

Whilst the primary time point for analyses is 15 months the 3D trial will also consider the potential effectiveness of the 3D intervention at 9 months. Secondary analyses will consider the primary and secondary outcomes at 9 months, rather than employing repeated measures analyses which would estimate the effectiveness of the 3D intervention over the duration of the study and examine if there was a differential effect across time. It is plausible that the 3D intervention will be effective in the short-term only with any effects disappearing by 15 months, this may still warrant its implementation into primary care practice and so its effectiveness at 9 months should be formally tested within this study.

The table below lists the secondary outcomes to be considered in analyses and the time points at which they will be measured (T0=baseline; T1=9 months; T2=15 months). Analyses for each secondary outcome will include adjustment for the relevant measure at baseline (T0).

Table 2: Secondary outcomes to be collected in the 3D study, to be compared between trial arms

Secondary outcome	Source	Scale	Time point		
			т0	T1	T2
Experience of holistic patient-centred care					
CARE measure of relational empathy (GP)	Questionnaire - 10 items	10-50	~	~	1
CARE measure of relational empathy (nurse)	Questionnaire - 10 items	10-50	\checkmark	Х	1
Care related to patients' priorities (LTC6)	Questionnaire – 1 item	1-4	✓	~	1
Care which is joined up (LTC6)	Questionnaire – 1 item	1-4	1	1	~
PACIC measure of chronic disease management	Questionnaire - 20 items	1-5	~	1	1
Overall satisfaction	Questionnaire – 1 item	1-5	1	1	1
Burden of illness measures					
EQ5D-5L	Questionnaire -5 items		✓	~	X
Self-rated health	Questionnaire – 1 item	1-5	\checkmark	\checkmark	1
Bayliss measure of illness burden	Questionnaire – 27+ items	0-145 ²	\checkmark	\checkmark	1
HADS Anxiety score	Questionnaire - 7 items	0-21	\checkmark	✓	1
HADS Depression score	Questionnaire - 7 items	0-21	\checkmark	✓	~
Burden of treatment			1		
Multimorbidity Treatment Burden Questionaire ³	Questionnaire - 10 items	0-100	~	1	1
Medication adherence: MMAS-8	Questionnaire - 8 items	0-8	✓	~	1
Number of drugs prescribed ⁴	Practice records	≥0	\checkmark	X	~
Number of high risk prescribing indicators	Practice records	≥0	\checkmark	X	1
Process measures ⁵					
Continuity of care - COC index	Practice records	0-1	\checkmark	X	1

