3.2.2 Secondary outcomes

CARE – 10 item questionnaire (each scored between 1-5), total score is summation of individual scores.⁹

PACIC – 20 item questionnaire (each item scored 1-5), overall score is an average of all 20 items.¹⁰

EQ5D-5L (at 9 months): As calculated for patients in primary outcome.

Bayliss – For each of 27 chronic conditions respondents select those that they experience and rate each selected condition on a five-point scale from 1 (interferes with daily activities "not at all") to 5 (interferes with daily activities "a lot"). Respondents are additionally allowed to add medical conditions not already on the list. The overall score representing level of morbidity is then the sum of conditions selected weighted by the level of interference assigned to each (that is, the sum of the interference scores).¹¹

HADS: Anxiety score – simple addition of the relevant 7 questions; Depression score – simple addition of the relevant 7 questions.¹²

Multimorbidity Treatment Burden Questionnaire – 10 items each scored 0-4. Total score is calculated by calculating the average score for each patient and then multiplying by 2.5 to get a value 0-100.

MMAS – 8 item questionnaire, with 7 questions being binary outcome assigned values 0 or 1, and a single question has values 4, 3, 2, 1 or 0. Questions 1-4 and 6-7 are coded 0 for 'yes' and 1 for 'no'; question 5 is coded 0 for 'no' and 1 for 'yes'. To get total score, add 7 binary questions together, and divide value of other single question by 4, and add them together to get a score between 0-8.¹³

Number of high risk prescribing indicators – This is the number of adverse warnings triggered and can be from 0 upwards.¹⁴

Continuity of care: Visit entropy will be used to measure the continuity of care.

A patient's visit to a healthcare provider can be considered a discrete random variable X. Then X can take on k distinct levels, one for each healthcare provider the patient could visit. It has a probability distribution function p(x) that represents the probability of visiting each healthcare provider.

Visit Entropy H(X) of a discrete random variable X can be calculated as¹⁵:

$$H(\mathbf{X}) = -\sum_{i=1}^{k} p(x_i) \log_2 p(x_i)$$

and the probability of visiting the ith provider is estimated as:

$$\hat{p}(x_i) \approx \frac{n_i + 1/k}{N+1}$$

Where n_i is the number of observed visits to the i^{th} provider, k is the total number of possible providers, and N is the total number of observed visits.

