H(X) approaches its minimum value of zero when a patient has perfect continuity of care, visiting only their primary physician, and approaches its maximum when there is no continuity of care.

Visit entropy is a relatively new measure, and is less well recognised than other measures for continuity of care. For this reason, continuity of care index (COCI) will also be considered for comparison.

Continuity of care index (COCI) formula¹⁶:

$$COCI = \frac{(\sum_{j=1}^{M} n_j^2) - N}{N(N-1)}$$

Where N is the total number of visits; n_j is the number of visits to the jth different provider, where j= 1, 2, 3, ... M, and M is the number of potential available providers.

Carers' experience scale – 6 item questionnaire (each item has 3 possible responses). Preference-based index values are available to transform the 6 responses to a profile measure value between 0 and 100^{17} .

EQ5D-5L (carers): As calculated for patients in primary outcome.

Multimorbidity Treatment Burden Questionnaire (carers) – development of final scoring system still under-development.

Quality of disease control – This is based on the Quality and Outcomes Framework (QOF) indicators and uses the 'patient average' method of Reeves *et al*¹⁸. It will be measured as a percentage for each individual patient, where it represents the percentage of QOF chronic disease management indicators that apply to that patient which were successfully met.

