3.3. Procedures for missing data

Missing data may arise as some participants may not return their questionnaires. It is anticipated that proportions with missing data will be similar between the two randomization arms but this will be examined and reported. Baseline characteristics will be compared between participants with and without 15-month follow-up data. In all tables missing data will be indicated by footnotes.

The primary analysis for EQ5D-5L (section 6.2) will include the full analysis set (section 3.1), including all patients in the groups to which they were allocated and imputing missing data. Reasons for missingness will be explored. Missing data will be imputed using multiple imputation techniques such as multiple imputation by chained equations (MICE). Imputation models will include baseline, 9 month and 15 month EQ5D-5L data (as available), intervention arm, stratifying/minimisation variables, as well as other variables such as baseline covariates and auxiliary covariates that are informative of missingness. To allow for clustering in Stata, imputations will be used for the primary analysis and the economic evaluation if possible. The influence of missing data on the primary analysis will be investigated in sensitivity analyses using complete case data only (section 6.5).

The analyses of secondary outcomes will use complete case data only. The only exception to this is for secondary outcomes derived from several items within a validated questionnaire, where questionnaire guidelines specifically state that an overall score can be derived even in the presence of missing data for one (or more) item(s). For example, for HADS anxiety and depression scores, questionnaire guidelines state that the score for a single missing item from a subscale is inferred by using the mean of the remaining six items; however, if more than one item is missing from that subscale the overall score is missing (and the observation excluded from the analysis). The numbers (percentage) of missing data will be presented in tables of secondary outcomes.

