6.3. Secondary analyses

All analyses of secondary outcomes will be adjusted for the baseline measure of the outcome (if available) and minimisation variables. Patient level analyses will also adjust for practice (as a random effect). All secondary outcomes will be considered at 9 and 15 months.

The list of variables and planned models of analysis are given in the table below. Distributional checks will be carried out for all outcomes and the most appropriate models selected (for example, for ordinal outcomes mixed-effects ordered logistic models will be performed and assumptions regarding the ordinal nature of responses tested; if not valid alternative multinomial models will be employed). The effect, 95% confidence interval and P value will be reported for each model along with the ICC if possible.

Table 6: Planned analyses - Patient level secondary outcomes

Outcomes	Type of variable	Type of model ¹
CARE measure of relational empathy (GP)	Continuous	Mixed-effects linear regression
CARE measure of relational empathy (nurse)	Continuous	Mixed-effects linear regression
Care related to patients' priorities (LTC6)	Discrete (ordinal)	Mixed-effects ordered logistic regression
Care which is joined up (LTC6)	Discrete (ordinal)	Mixed-effects ordered logistic regression
PACIC measure of chronic disease management	Continuous	Mixed-effects linear regression
Overall satisfaction	Discrete (ordinal)	Mixed-effects ordered logistic regression
EQ5D-5L	Continuous	Mixed-effects linear regression
Self-rated health	Discrete (ordinal)	Mixed-effects ordered logistic regression
Bayliss measure of illness burden	Continuous	Mixed-effects linear regression
HADS Anxiety score	Continuous	Mixed-effects linear regression
HADS Depression score	Continuous	Mixed-effects linear regression
Multimorbidity Treatment Burden Questionnaire	Continuous	Mixed-effects linear regression
Medication adherence: MMAS-8	Continuous	Mixed-effects linear regression
Number of drugs prescribed	Count data	Poisson regression random effects
Number of high risk prescribing indicators	Count data	Poisson regression random effects
Continuity of care - COC index	Continuous	Mixed-effects linear regression
Continuity of care - Visit Entropy	Continuous	Mixed-effects linear regression
Quality of disease management	Continuous	Mixed-effects linear regression
Number of hospital admissions	Count data	Poisson regression random effects
Number of outpatient attendances	Count data	Poisson regression random effects

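### Complete-case handling plus compulsory baseline adjustment drops patients who have a secondary outcome at follow-up but no T0 value

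*SAP*

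**What the plan says.** Section 3.3 of the SAP sets the rule for missing data in secondary outcomes: "The analyses of secondary outcomes will use complete case data only". It allows one departure: "The only exception to this is for secondary outcomes derived from several items within a validated questionnaire", where the questionnaire's own guidelines permit a score with one or more items missing. That covers missing items, not a T0 score that is missing altogether. Imputation is kept for the primary outcome ("The primary analysis for EQ5D-5L (section 6.2) will include the full analysis set (section 3.1") and, if possible, the economic evaluation.

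Section 2.10.2 makes baseline adjustment unconditional: "Analyses for each secondary outcome will include adjustment for the relevant measure at baseline (T0". Table 2 lists a T0 measurement for every patient secondary outcome. Section 6.3 repeats the rule with a qualifier: "All analyses of secondary outcomes will be adjusted for the baseline measure of the outcome (if available) and minimisation variables".

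Section 3.1 defines the complete cases set as consenting patients whose missing data are not imputed. It does not say which variables must be observed for a patient to count as complete.

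**The concern.** A randomised comparison needs the follow-up outcome to be observed. The baseline value is a covariate that improves precision, and its absence need not cost the patient. Under sections 3.3 and 2.10.2 read together it does: a model containing the T0 covariate, fitted without imputation, omits every row in which that covariate is missing. Follow-up data already collected are discarded.

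The qualifier in section 6.3 does not settle the matter. If it refers to the outcome, it changes nothing in Table 2, where every outcome has a T0 measurement. If it refers to the patient, the SAP does not say how a patient without a T0 value enters an adjusted model. Section 1 says the plan should let someone else carry out the analysis, yet two analysts could reach different denominators.

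Precision is at stake, and so is the population to which each secondary estimate applies. One internal comparison is also affected. Section 3.2.2 adds COCI for comparison with visit entropy, but the two measures treat patients with few baseline visits differently.

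**Working it through.** **1. Which outcomes are exposed**

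| Outcome group (Table 2) | Source | Can T0 be missing when follow-up is present? |
|---|---|---|
| CARE, LTC6, PACIC, satisfaction, EQ5D-5L at 9 months, self-rated health, Bayliss, HADS, treatment burden, MMAS-8 | Questionnaire | Yes, if the T0 score is missing |
| COCI | Practice records | Yes, if there were 0 or 1 visits in the baseline period |
| Visit entropy, number of drugs, high-risk prescribing, quality of disease management | Practice records | Largely not |
| Admissions, outpatient attendances | CSU data if available, otherwise questionnaire | Largely not where CSU data are used |

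One consequence concerns EQ5D-5L. A patient who lacks only the baseline value is kept by imputation in the primary 15-month analysis but lost from the secondary 9-month analysis of the same instrument.

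**2. COCI against visit entropy**

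The COCI formula in section 3.2.2 is (Σn_j² − N) / [N(N − 1)]. The SAP defines its terms thus: "Where N is the total number of visits; n_j is the number of visits to the jth different provider".

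- N = 0: (0 − 0)/(0 × −1) = 0/0, undefined.
- N = 1: (1 − 1)/(1 × 0) = 0/0, undefined.
- N = 2, same provider: (4 − 2)/(2 × 1) = 1.

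Visit entropy uses p_i = (n_i + 1/k)/(N + 1). With k = 5 providers, chosen for illustration:

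- N = 0: every p_i = 0.2, so H = log2(5) = 2.32.
- N = 1: one p = 1.2/2 = 0.6 and four p = 0.2/2 = 0.1, so H = 1.77.

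The same patient therefore has no baseline COCI but does have a baseline visit entropy. The patient leaves the first model and stays in the second.

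**3. The plan's own power figure**

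Inputs from section 2.7: 32 practices, 1382 participants, 80% followed up, ICC 0.03, effect 0.274 SD, 5% significance (taken as two-sided).

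- Analysed: 1382 × 0.8 = 1105.6; per practice m = 1105.6/32 = 34.55.
- Design effect: 1 + (34.55 − 1) × 0.03 = 2.0065.
- Effective number per arm: 552.8/2.0065 = 275.5.
- Power: Φ(0.274/√(2/275.5) − 1.96) = 0.895, which agrees with the stated figure of around 90%.

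**4. Loss of precision**

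With m analysed patients per practice, the variance of a practice mean is proportional to ICC + (1 − ICC)/m. The share lost is not in the SAP, so the shares below are assumptions.

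| Share lost | m | 0.03 + 0.97/m | SE ratio |
|---|---|---|---|
| 0 | 34.55 | 0.0581 | 1 |
| 10% | 31.10 | 0.0612 | 1.027 |
| 15% | 29.37 | 0.0630 | 1.042 |
| 25% | 25.91 | 0.0674 | 1.078 |

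On the power scale, with the primary outcome's inputs borrowed for illustration, 0.895 falls to 0.880 at 10% loss, 0.859 at 20% and 0.833 at 30%.

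**5. Bias or change of population**

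A simulation used 32 practices of 35 patients, with 10%, 20% or 30% of baselines missing independently of arm and models fitted by least squares. With the same effect for everyone, complete case and the missing-indicator method were both unbiased. The standard error was about 2% to 8% larger for complete case. When the effect was assumed to be twice as large in patients without a baseline score, complete case still returned 0.27 to 0.28, the effect in those with a score. The whole-sample effect was then 0.274 × (1 + share missing) = 0.30, 0.33 and 0.36. The doubling is an assumption with no source in the SAP; it only shows what kind of change is possible.

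**The case against.** Complete case for secondary outcomes is an explicit, pre-specified choice. Imputation is kept for the primary outcome, and missing numbers will be reported. The qualifier in section 6.3 can be read at patient level. The assumed losses raise standard errors only modestly, and the share affected may be small: eligibility requires three or more listed conditions, and section 2.5 describes usual care as recall to separate clinics. The indicator method also has a condition, namely that baseline missingness is unrelated to arm. Section 2.6 places randomisation after invitations are mailed, and the SAP does not say that baseline questionnaires are returned before allocation.

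Much of this stands as a limit on size. It does not remove the gap, because no reading of section 6.3 supplies a method. If baseline missingness did depend on arm, complete case would be exposed too.

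A reader might infer more than the document supports:

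- **That everyone who had not seen a nurse or GP is removed from the CARE analyses.** The SAP says only "CARE – 10 item questionnaire (each scored between 1-5), total score is summation of individual scores". It has no rule for a patient with no consultation to rate, so for "CARE measure of relational empathy (nurse" and its GP counterpart the link to visits is an inference. It is exact only for COCI.
- **That mean consultation duration is caught by the same rules.** It is a process measure (Table 4, section 6.4), and the sentences at issue name secondary outcomes only.
- **That precision is lost across all secondary outcomes.** Baselines taken from records are largely unaffected.
- **That the patients lost are low users who would gain most from the intervention.** Nothing in the SAP shows this.

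**Conclusion.** The point holds. Sections 3.3 and 2.10.2 together exclude patients who have a valid follow-up score but a missing or undefined T0 score, and section 6.3 does not say how they would be kept. Questionnaire outcomes and COCI are mainly affected, and the planned comparison of COCI with visit entropy would rest on different patients.

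The size is modest and conditional. Standard errors would be about 3%, 4% or 8% larger if 10%, 15% or 25% of otherwise usable patients were lost, given the ICC and practice sizes of section 2.7, which were set for the primary outcome. The estimates would also describe a narrower population. Bias between arms is not demonstrated: with baseline missingness unrelated to arm and a uniform effect, complete case is unbiased.

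**What to change.** Amend sections 3.3 and 6.3 as follows, and bring section 2.10.2 into line:

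- Define the analysis set for each secondary outcome as all patients with that outcome observed at the follow-up time in question.
- Where the T0 value is missing or undefined, set the baseline covariate to a constant (for example its mean) and add a missing-baseline indicator to the model.
- Replace the qualifier in section 6.3 with this rule.
- Report, for each outcome and by arm, how many patients lack a T0 value. State whether baseline questionnaires were returned before allocation.
- Keep strict complete case as a sensitivity analysis.

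The cost is a few sentences, one extra term per model and no new data. Adjustment is slightly weaker for the retained patients, and the method relies on baseline missingness being unrelated to arm, which the report by arm would check. The change does not help where COCI is undefined at follow-up itself, so its denominator should still be shown beside that of visit entropy.

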3.4. Study centre effects

Randomisation is at the general practice (centre) level; the effect of practice will be taken into account as a random effect in multi-level regression models.

3.5. Outliers

Data will be checked for validity, each variable will be examined separately, and any outliers (> 3SD of the mean) will be checked for entry errors. Where no error is found, the variable will be checked for concordance with other variables, differences will be noted. We will also examine for influential observations (Cooks distance¹⁹) in the main analysis models. Outliers and influential observations will be noted. Sensitivity analyses removing outliers will be conducted.

3.6. Data cut-off

The cut-off for outcome data to be included in the analyses is 30 June 2017.

4. DESCRIPTION OF PARTICIPANT CHARACTERISTICS

4.1. Disposition

A flow of clusters (general practices) and participants through the trial will be summarised in a CONSORT diagram that will include the eligibility, reasons for exclusion, patients consenting, practices randomised to the two treatment groups, losses to follow up and the numbers analysed (for the primary outcome).

4.2. Baseline characteristics

The distributions of continuous variables will be examined. If data are approximately normally distributed, then the variable will be summarised in terms of the mean and standard deviation. For continuous variables that are not normally distributed median and inter quartile range (IQR) will be presented to summarise the variable. Categorical data will be summarised in terms of frequency counts and percentages. We will summarise all variables by trial arm, at both the cluster (practice) level and individual-level summary data. No formal statistical comparisons will be undertaken.

5. ASSESSMENT OF STUDY QUALITY

5.1. Eligibility checks

The numbers of patients who were eligible (identified as having multimorbidity), randomly selected, invited to participate (some excluded due to terminal illness for example), and agreeing to participate in the trial (and reasons for exclusion/no consent) will be reported in the CONSORT Flow Diagram. Amongst those eligible and invited to participate, socio-demographic and baseline characteristics will be compared between those consenting and those either refusing consent/not responding.

5.2. Study completion

Final follow up is at 15-month post-randomisation. The numbers of patients followed-up and lost to follow-up will be reported for each treatment arm in the CONSORT Flow Diagram.

5.3. Compliance/ Fidelity

Fidelity will be considered and examined in detail within the process evaluation (qualitative aspects of the process evaluation will be described elsewhere). Quantitative measures are detailed in Table 5 above and will be reported for the 3D intervention group only.

Compliance (at the patient level) will be defined as 'full' – two GP 3D appointments and two nurse 3D appointments attended; 'partial' – at least one GP or nurse 3D appointment attended, but not full attendance; and 'none' – no GP 3D appointment and no nurse 3D appointment attended. The percentage of patients in each of these categories will be reported for the 3D intervention arm.

5.4. Protocol deviations

Any protocol deviations will be fully documented.

6. ANALYSIS OF EFFECTIVENESS

The reporting and presentation of data from this trial will be in accordance with the CONSORT guidelines for cluster randomized trials²⁰. STATA 14.1 will be used for all statistical analysis.

6.1. Summary of primary and secondary outcomes

The primary outcome will be summarised for each treatment group as the mean (SD) or median (IQR) as appropriate. Continuous secondary outcomes will be summarised as mean (SD) or median (IQR) as appropriate. Binary/ordinal data will be summarised in terms of frequency counts and percentages.

